12.4 Statistical Analysis and Sensitivity Tests

To ensure robust conclusions, we will apply multiple sensitivity analyses, in addition to ITT and PP analyses:

1. Complete Case Analysis (excluding patients with missing data).
2. Multiple Imputation of missing data to assess the impact of lost-to-follow-up cases.
3. Scenario analysis excluding non-neurological deaths.

Safety analysis

For each patient and each type of toxicity described according to the CTCAE (V.5.0), the worst-case category identified during treatment will be used for the descriptive analysis.

Safety Measures

Safety will be assessed using:

- Incidence of treatment-related adverse events (TEAEs)
- Incidence and severity of treatment-emergent adverse events (TEAEs)
- Incidence of serious adverse events (SAEs)
- Incidence of TEAEs and SAEs leading to discontinuation of study medication.
- Changes in blood chemistry, hematology and coagulation parameter results
- Changes in vital signs including temperature, pulse, respiratory rate, systolic and diastolic blood pressure
- Changes in physical examination results
- Changes in electrocardiogram (ECG) results

These data will be described using lists and tables.

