2.5 Identification and description of the experimental medication or medications

Cilostazol is a selective inhibitor of phosphodiesterase 3 (PDE 3) and antiplatelet agent. It is available in a tablet form and can be administered orally or through a gastric tube after being crushed.

"CASH" protocol, version 2.1 of 04/04/2025

2.6 Description and justification of the dosage, administration method, administration design and treatment period.

Patients will be included within the first 96 hours after SAH onset and randomly assigned to either cilostazol or placebo group. The dose of cilostazol will be 100mg twice a day for 14 days,.

The dosage of cilostazol is similar to the one tested in the four previous trial that documented benefit¹²⁻¹⁵.

Pharmacokinetics justification

We reviewed ten human studies that have directly quantified cilostazol's pharmacokinetics under varied dosing and design protocols. In healthy volunteers—primarily Korean subjects—one study reported an AUC of $12,100 \pm 4,880 \text{ ng}\cdot\text{h}/\text{ml}$, while Cmax values ranged from 283.7 to 1,623.9 mg/ml over doses from 25 to 300 mg. Elimination half-life consistently approximated 11 hours, and Tmax varied between 2.4 and 4 hours; one report estimated apparent clearance (CL/F) at 12.8 l/h.¹⁷⁻²⁶

Genetic analyses indicate that CYP3A5 and CYP2C19 variants significantly affect clearance and half-life, whereas ABCB1 appears to have no effect, overall the variance explained by polymorphism was 7% underlining a relevant but limited effect of genetics on cilostazol pharmacokinetics. A study in subjects aged 50 and older found no significant influence of age or gender. Investigations of drug interactions reveal no notable pharmacokinetic change when cilostazol is co-administered with probucol, but co-administration with simvastatin increases simvastatin AUC by 64% and its active metabolite by 31%. The drug will be delivered in oral form if patient is able to swallow the tablet. If not, tablets will be crushed by the nurse in charge of the patient, and given by oral or enteral route through feeding tube if required. Administration of crushed tablet will be standardized at specific timing in each center. In case a patient can eat a meal, the delay between administration and meal will be of 30 minutes minimum

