5.2 Follow-up Visits

Follow up visits will be performed daily from day 1 to day 28. One Brain imaging will be realized 24/48 hours after the aneurism treatment and one between day 28 and 45 after randomization. Transcranial doppler, MR CTA or DSA results will be collected when realized.

Day 1 to day 28

Vital status

Compliance to treatment

Experimental Treatment administration will be collected daily

Safety follow up

- Any major Cilostazol-related adverse event will be assessed:
 - Arrhythmia from auricular origin
 - Arrhythmia from ventricular origin
 - Abnormal bleeding
 - Allergy
- Other minor Cilostazol-related adverse events:
 - Tachycardia,
 - Fever
 - Fainting
 - Nausea
 - Vomiting
 - Stomach pain

Cerebral vasospasm

- Blood flow velocity increase on TCD
- Cerebral vasospasm diagnosed upon MR/CTA or DSA and its severity (mild/moderate/severe)

Delayed cerebral ischemia

- New focal deficit
- Glasgow point decrease
- No other cause

Treatment in the last 24 hours

- Continuous sedation
- Mechanical ventilation
- Extraventricular drain
- Therapy Intensity Level (TIP) for Raised ICP treatment (See Appendix 7)
- Hypertension therapy
- Vasopressors (epinephrine/norepinephrine/dobutamine)
- Milrinone administration
- Endovascular treatment (Balloon therapy or vasodilatator administration)
- Other treatment
- At ICU discharge, the modified Rankin scale will be evaluated by a blinded research technician in case of lost to follow up.

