5.5 Table or diagram summarising the chronology of the research

Actions	Inclusion visit	Day 0-28	End of research 6 months
Informed consent	x		
History	x		
Clinical exam*	x	x	x
Para-clinical exam*	x	x	x
Medical procedures (ECG, etc.)			
Dispensation of treatments		x	
Compliance	x	x	x
Adverse events		x	x

*A complete description of Clinical exam, paraclinical exam and tests are described specifically in each visit in section 5.1 to 5.3

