5.8 Termination rules

5.8.1 Criteria and methods for prematurely terminating the research treatment

5.8.1.1 Different situations

- Temporary termination of treatment, the investigator must document the reason for stopping and restarting the treatment in the subject's source file and the case report form (CRF)
- Premature termination of treatment, but the subject is still included in the research, until the end of the subject's participation, the investigator must document the reason (if during the administration period, the patient get out of the ICU, the treatment will stop).
- Premature termination of treatment and end of participation in the research.

The investigator must:

- o Document the reason(s)
- o Collect the assessment criteria when participation in the research ends, if the subject agrees
- o In case of severe adverse event, subject will be closely monitored and followed.

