7 TREATMENT ADMINISTERED TO RESEARCH PARTICIPANTS

7.1 Description of the experimental medication or medications

7.1.1 Experimental medication 1

Cilostazol 100mg tablets

Packaging type : blisters

Two times a day (every 12 hours) for 14 days, 28 tablets in total

Storage: room temperature

Shelf life: 3 years

Oral form if patient is able to swallow the tablet. If not, tablets will be crushed by the nurse in charge of the patient, and given by oral or enteral route through feeding tube if required. Of note administration of crushed tablet will be standardized at specific timing in each center. In case a patient can eat a meal, the delay between administration and meal will be of 30 minutes minimum

Of note a market authorization (Autorisation de Mise sur le Marché) is available in France for cilostazol in chronic arteritis but no marketed anymore since 2010 in France. The GHU Paris Psychiatry and Neurosciences pharmacy will import cilostazol which is also marketed in Europe. The blinding as well as the creation of a placebo will be subcontracted to a competent GMP establishment. The logistic will be centralized by the pharmacy of the GHU Paris and the pharmaceutical circuit will be co-constructed between GHU Paris and pharmacies of the different investigator centres (storage and delivery).

7.2 Description of the non-experimental treatment or treatments (medications required for carrying out the research)

7.2.1 Non-experimental medication 1

As recommended by French and European guidelines, a preventive medication of DCI by nimodipine has to be administered during the ICU stay. The posology, route (IV or enteral) and length of treatment is left to the discretion of the caring physician.

7.3 Description of the traceability elements that accompany the experimental medication or medications

Designated pharmacists responsible for the receipt, handling and dispensing of study drugs (active and placebo) will maintain study drug records during the study: details of how all phases of dispensing and withdrawal of unadministered drugs will be monitored and controlled, and the patient code/kit code correspondence will be described in the Pharmacy Manual to be established prior to the start of the study.

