10.3.5 Period for notifying the sponsor

The investigator must report all SAE that occur in research subjects:

- after the date on which treatment with an experimental medication began
- throughout the period during which the participant is monitored, as determined by the research
- for up to 4 or more weeks after the participant stops treatment using the experimental medication
- with no time limit, if the SAE is likely to be due to the experimental medication or to the research procedures (for example, serious reactions that could appear long after exposure to the medication, such as cancers or congenital abnormalities).

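### The worst-grade toxicity table stops when study drug stops, so it omits later events and worsening, over a window that differs by patient and is set after randomisation

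*Protocol*

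**What the plan says.** Under the safety analysis in section 12.4, toxicity is described by CTCAE (v5.0) for each patient and each toxicity type, and "the worst-case category identified during treatment will be used for the descriptive analysis". The phrase is not defined there and no period after the last dose is added.

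The treatment period is short and can be shorter still. Section 7.1 gives "Two times a day (every 12 hours) for 14 days, 28 tablets in total". Section 5.8.1.1 adds that "if during the administration period, the patient get out of the ICU, the treatment will stop", and section 5.8.2 provides for stopping because of a serious adverse event.

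Collection runs longer. Section 5.2 states "Follow up visits will be performed daily from day 1 to day 28" and, under that heading, "Any major Cilostazol-related adverse event will be assessed", followed by a list of minor events. The schedule in section 5.5 marks the row "Adverse events" at days 0-28 and again at 6 months. Section 10.3.5 has serious events reported "for up to 4 or more weeks after the participant stops treatment using the experimental medication", and section 10.3.4 has events followed to resolution.

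**The concern.** The rule for the table is narrower than the collection plan, and the end of the window is partly decided by the outcome. A toxicity that leads to stopping also closes the period in which its grade is read. Suppose a bleed is moderate on day 5, study drug is stopped that day, and the bleed is fatal on day 7. Taken literally, the rule enters this patient as moderate. A patient who leaves the ICU on day 6 has a six-day window; one who stays has fourteen. Worst grades compared between arms over windows of unequal length, set after randomisation, are not a clean comparison. Section 4.2.1 says the trial is to show that the combination is safe as well as superior, and this is the only per-patient severity rule in the safety section.

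**Working it through.** The protocol gives no figure to reproduce here. The check compares the two windows and then asks how much early stopping would be needed to distort the comparison.

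**Windows.**
- Full course (section 7.1: 14 days; section 5.2: day 28): (28 − 14)/28 = 50% of calendar days fall outside the rule.
- Stop on day 5 (an illustrative date): (28 − 5)/28 = 82%.

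**Drug remaining after the last dose.** Section 2.6 says: "Elimination half-life consistently approximated 11 hours".
- At 24 h: 0.5^(24/11) = 0.22.
- At 48 h: 0.5^(48/11) = 0.05.
- Five half-lives: 5 × 11 = 55 h, or 55/24 = 2.3 days.

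A window with no lag therefore excludes about two days with drug still present. Most of days 15-28 is off drug.

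**Effect on the arm comparison (assumed values).** The protocol gives no event rates by day and no stopping rates. Assume a constant daily hazard h, so that incidence by day d is 1 − exp(−h·d). Assume 20% incidence by day 28 on placebo, so h = −ln(0.8)/28, and that all placebo patients are treated for 14 days.

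- Placebo, on treatment: 1 − exp(−14h) = 10.6%, which is 53% of the patients with an event by day 28. The share is 51% if the 28-day incidence is 10%, and 54% if it is 30%.
- Let a fraction q of the cilostazol arm stop on day s, independently of the event. Write A14 and As for cilostazol incidence by days 14 and s, and P14 for placebo incidence by day 14. The on-treatment figures are equal when q = (A14 − P14)/(A14 − As).

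| Assumed hazard ratio | Cilostazol by day 28 (placebo 20%) | Cilostazol on treatment, no early stops (placebo 10.6%) | q for equality, stop day 3 | q for equality, stop day 7 |
|---|---|---|---|---|
| 1.1 | 21.8% | 11.6% | 11% | 18% |
| 1.25 | 24.3% | 13.0% | 24% | 39% |
| 1.5 | 28.4% | 15.4% | 41% | 66% |
| 2.0 | 36.0% | 20.0% | 62% | 100% |

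With equal treatment duration the order of the arms is kept. Below the q shown, the difference shrinks; above it, the more toxic arm looks milder. The model counts events only. It does not include a rise in grade after stopping, which is lost without any such threshold but cannot be sized from the protocol.

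**The case against.** A reader might infer that the data from days 15-28 are discarded. They are not. Section 12.4 also lists incidence and severity of treatment-emergent events, incidence of serious events, and events leading to discontinuation, none limited to the treatment period. Section 4.1.2 makes 28-day mortality (criterion 8) and major and minor cilostazol-related events (criteria 12 and 13) secondary criteria. The fatal bleed in the example would appear as a serious event, a discontinuation, a major bleed and a 28-day death. This stands, with one limit: the window for treatment-emergent events is not defined in the protocol, and serious-event incidence does not show worst grade by toxicity.

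A reader might also infer that the table is biased towards cilostazol whenever cilostazol causes stops. The protocol does not support that. A toxicity that triggers stopping begins on treatment and is counted; only a later rise in grade or a later new event is missed. A reversal needs markedly more early stopping in one arm, and stopping at ICU discharge applies to both blinded arms.

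Nor are the 50% and 82% shares of observed data. The opening of section 5 describes daily visits only during the ICU stay, with one visit at day 28 after discharge, whereas section 5.2 reads as daily for everyone. The percentages are calendar days.

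A longer window has its own cost. Section 10.3.3.1 expects delayed ischaemia up to day 21, hydrocephalus, nosocomial infection and about 30% mortality from the disease itself. Counting these in both arms can dilute a drug effect. This stands, and is the reason to keep an on-treatment display.

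Finally, defining the treatment period and any lag is ordinary SAP content, and the SAP is not shown. That would answer a missing detail. Here the protocol states a rule, and the rule as worded ends with treatment.

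**Conclusion.** The point holds for the worst-grade table. As worded, it omits new events and worsening after study drug stops, and its window varies between patients for reasons arising after randomisation. It may understate severity in an arm with more early stopping. For a completed course, half of the 28 calendar days lie outside it. Under the assumed constant hazard, the 14-day window holds 51% to 54% of patients with an event by day 28. Whether the arm comparison is distorted depends on stopping rates by arm, which the protocol does not give. The table is descriptive, other outputs report the same harms, and the primary analysis and sample size are untouched. It is a moderate point that should be corrected because the correction is simple.

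**What to change.** In section 12.4 and the SAP, report the worst CTCAE category per patient and toxicity type from first dose to day 28, for every patient in the safety population, whatever the date of stopping. Keep the on-treatment table as a supplement, with a stated lag after the last dose justified from the half-life in section 2.6. Do not extend the main table to four weeks after the last dose: that limit would fall on day 33 after a stop on day 5 (5 + 28) and day 42 after a full course (14 + 28), which brings back a window that depends on the patient. Later serious events remain in the serious-event output.

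Reconcile the opening of section 5 with section 5.2, so that it is clear whether events after ICU discharge are collected daily or only at the day 28 visit. Confirm too that CTCAE categories can be assigned throughout this window, since sections 10.3 and 10.3.2.2 grade events as mild, moderate or serious.

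The cost is one sentence in section 12.4 and one clarification of the visit schedule. The statistical cost is more background events of the haemorrhage in both arms, which may dilute a drug effect; the supplementary table lets the reader judge this.

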12.5 Sample size estimation

To estimate the sample size, as no direct efficacy studies of cilostazol versus nimodipine or in combination with nimodipine versus placebo were available, a literature search was conducted to verify the possibility of performing a network meta-analysis that would allow an evaluation for indirect comparisons.

Reference is made to a network meta-analysis [Dayyany, 2022] on prophylactic therapies for cerebral vasospasm secondary to SAH.

The literature search of the referenced network meta-analysis stopped in February 2020; therefore, an update was performed on Medline according to the same strategies from February 2020 to December 2022.

Therefore, for the network meta-analysis, trials using nimodipine, cilostazol or fasudil (the usual comparator or in combination with cilostazol) as prophylaxis in at least one arm of the study were selected. Concerning the outcome as per the main objective of the CASH study (mRS assessed at six months, where the favourable outcome is defined as the mRS score of 0 to 2, and unfavourable outcome of 3 to 6) for the studies where the assessment was made using the GOSE, the results were converted as in Table 1. The meta-analysis was performed with MetaXL Version 5.3[1], a fixed-effects model was used, and the method for calculating the weighted average effect was the inverse of variance heterogeneity. The global heterogeneity of the model was assessed using the H inconsistency index [2].

The selected studies, the model description, and the results are reported in Appendix 8.

Table 1. GOSE vs mRS conversion table

Modified Rankin Scale (mRS)	Glasgow Outcome Scale (GOS)
0 - No symptoms.	
1 - No significant disability. Able to carry out all usual activities, despite some symptoms.	4 - Moderate disability
2 - Slight disability. Able to look after own affairs without assistance, but unable to carry out all previous activities.	5 - Low disability
3 - Moderate disability. Requires some help, but able to walk unassisted.	
4 - Moderately severe disability. Unable to attend to own bodily needs without assistance, and unable to walk unassisted.	1 - Death
5 - Severe disability. Requires constant nursing care and attention, bedridden, incontinent.	2 - Persistent vegetative state
6 - Dead.	3 - Severe disability

A total of 9 studies with a cumulative number of 1732 patients were included in the network meta-analysis; the details are given in Table 2.

Table 2: Trials selected for network meta-analysis and events for each study arm favourable outcome at the longest follow-up

Active	Control	Study name	Active			Control		
			Nb	Case s	Non-cases	Nb	Case s	Non-cases
Nimodipina	Placebo	Petruck, 1988	72	28	44	82	28	54
Nimodipina	Placebo	Pickard, 1989	27 8	223	55	276	185	91

Nimodipina	Placebo	Ohman, 1991	10 4	86	18	109	86	23
Fasudil	Placebo	Shibuya, 1992	13 6	98	38	136	95	41
Fasudil	Nimodipina	Zhao, 2006	33	27	6	34	28	6
Fasudil plus Nimodipine	Nimodipina	Zhao_2, 2011	55	49	6	60	48	12
Cilostazol plus Fasudil	Fasudil	Suzuki, 2011	49	39	10	51	24	27
Cilostazol plus Fasudil	Fasudil	Sembukuya, 2013	54	39	15	55	36	19
Cilostazol	Placebo	Matsuda, 2016	74	60	14	74	61	13
			85 5	649	206	877	591	286

[figure not shown]

Figure 1. Network plot

[figure not shown]

Figure 2. Forest plot

The network meta-analysis versus nimodipine, where the outcome is the patient's status at at the longest follow-up, shows a non-inferiority of fasudil versus nimodipine (OR=0.720; 95% CI unilateral lower bound =0.050).

The efficacy trend of the combination of fasudil plus cilostazol (OR= 2.25; 95% CI unilateral lower bound=0.705) and fasudil plus nimodipine (OR=2.04; 95% CI unilateral lower bound=0.840) compared to treatment with nimodipine alone appears to be sharper.

"CASH" protocol, version 2.1 of 04/04/2025

Considering that in both Japan and China, the standard prophylaxis after SAH is fasudil or fasudil plus cilostazol, considering only trials evaluating combination versus monotherapy with nimodipine or fasudil, the greater efficacy of combination therapy is apparent.

The results of the meta-analysis and the forest plot are reported below. A low heterogeneity was found ($I^2=0.45$; $p=0.16$); therefore, the inverse variance heterogeneity model was applied (Doi, 2015)

Study	OR	LCI 95%	UCI 95%	Weight (%)
Zhao, 2011 (fasudil plus nimodipine vs nimodipine)	2.042	0.709	5.880	24.322
Suzuki, 2011 (fasudil plus cilostazol vs fasudil)	4.388	1.809	10.641	34.665
Sembukuya, 2013 (fasudil plus cilostazol vs fasudil)	1.372	0.608	3.099	41.013
Pooled	2.261	1.108	4.614	100.000
Statistics				
I-squared	44.9			
Cochran's Q	3.63			
Chi2, p	0.163			

In light of the results obtained for the sample size estimation, an OR between the two arms of 1.86 is assumed as a precaution. This assumption sets the proportion of patients who will obtain a favourable outcome in the control arm at 65% and the proportion of responders in the experimental arm at least 76%. These proportions may appear high, but it should be noted that the study does not include patients with early death and without surgery.

The experimental design includes two intermediate analyses; a sequential group test and the O'Brian-Fleming Analog spending function for alpha and beta errors were used.

Therefore set unilateral alpha at 0.025 and the power of the test (1-beta) at 0.80, 284 patients are needed per experimental arm; details are given in table 3 and figure 1.

A drop-out rate of no more than 10% is expected so that the sample size will be 630 patients (315 per experimental arm).

All estimates for the interim analyses are made without considering the inflation quota for drop-out patients. Therefore this evaluation will be made at the planned number of patients who completed the study. Only the final analysis will bear any inflationary share of the sample.

Table 3. Summary Report -

Item	Value
Maximum Number of Stages (Design):	3
Current Stage:	0
Alternative Hypothesis:	$P1 - P2 < 0$ (one-sided)
Alpha Spending Function:	O'Brien-Fleming Analog
Beta Spending Function:	O'Brien-Fleming Analog
Futility Boundaries:	Binding
Target Alpha:	0.025
Alpha (from simulations):	0.025
P1:	0.65
P2:	0.76
N1 (if final stage reached):	284
N2 (if final stage reached):	284
Target Power:	0.8
Power (from simulations):	0.8016
Maximum Information:	692.8

Information Report

Maximum Information: 692.8519

 Alternative Hypothesis: $P1 - P2 < 0$ (one-sided)

Alpha: 0.0250

Stage	Target information proportion	Target sample size N1	Target sample size N2	P1	P2
1	0.33	95	95	0.65	0.76
2	0.67	189	189	0.65	0.76
3	1.00	284	284	0.65	0.76

Alpha Spending

Target Final Stage Alpha: 0.0250

Spending Function: O'Brien-Fleming Analog

Stage	Information proportion	Alpha spent this stage	Cumulative alpha spent	Percentage alpha spent at this stage	Cumulative percentage
1	0.33	0.0001	0.0001	0.4	0.4
2	0.67	0.0059	0.0060	23.8	24.2
3	1.00	0.0190	0.0250	75.8	100.0

Beta Spending for Futility

Target Cumulative Beta at Final Stage: 0.2000

Spending Function for Futility: O'Brien-Fleming Analog

Stage	Information proportion	Beta spent this stage	Cumulative beta spent	Percentage beta spent at this stage	Cumulative percentage
1	0.33	0.0264	0.0264	13.2	13.2
2	0.67	0.0901	0.1165	45.7	58.3
3	1.00	0.0835	0.2000	41.7	100.0

Boundary Probabilities for $\delta = -0.11$

Number of Simulations: 100000

Futility Boundaries: Binding

After Efficacy Boundary Crossing: Hold Out

After Binding Futility Boundary Crossing: Hold Out

 Alternative Hypothesis: $P1 - P2 < 0$ (one-sided)

P1: 0.65

P2: 0.76

 δ : -0.11

Stage	N1	N2	Efficacy		Futility	
			Boundary	Probability	Boundary	Probability
1	95	95	-3.7103	0.0253	0.2701	0.0277
2	189	189	-2.5111	0.4166	-1.1224	0.0885
3	284	284	-1.9308	0.3597	-1.9308	0.0821

Average N1: 226.

Average N2: 226

[figure not shown]

Figure 1.

12.6 Specify if subjects who leave the research prematurely will be replaced and in what proportion.

The primary outcome is assessed only one time 6 months after Day 0 (5 months and a half after last day of treatment) that could lead to patient's loss to follow up. Nevertheless, SAH is a serious condition that requires a long and close patient's monitoring. That will limit patient's loss to follow up. The patients who leave study prematurely (for loss to follow up or death) won't be replaced and will be considered as non responder patients in the main analysis of primary criterion.

Some sensitivity analyses will be performed with complete cases only.

Only, the particular circumstance of patient resignation will lead to exit patient of the primary analysis. A 10% rate of non evaluable patients is foreseen.

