4.2.4 Randomisation

After screening for inclusion and non-inclusion criteria, and obtaining consent, patients will be randomized (1:1 ratio) to cilostazol or placebo groups by logging onto a randomization website using a pre-prepared randomization list, balanced by randomly variable block size. Randomization will be stratified by centre, age (<50 years; >=50 and <=75 Years; >75 years); and severity (Fisher grade from I to III; Fisher grade IV)

"CASH" protocol, version 2.1 of 04/04/2025

Randomisation will occur in an online data entry platform, guaranteeing the concealment of the experimental arm assigned to the doctor performing the inclusion and randomisation of the patient.

The randomisation code will be disclosed once recruitment is completed.

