5.8.3 Methods for replacing subjects, if applicable

A 10 % dropout rate of patients has been estimated and considered for the calculation of the number of subjects to be included.

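### The 10% inflation from 284 to 315 per arm fits only patients who leave the analysis; under section 12.6 lost patients stay in as failures, so 0.80 power depends on an unstated split of the 10%

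*Protocol*

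**What the plan says.** Section 12.5 of the protocol gives the base calculation: "Therefore set unilateral alpha at 0.025 and the power of the test (1-beta) at 0.80, 284 patients are needed per experimental arm". The assumed favourable-outcome rates are 65% and 76%, and the simulated power of the three-look design is 0.8016. The next step is "A drop-out rate of no more than 10% is expected so that the sample size will be 630 patients", that is, 315 per arm. Section 5.8.3 repeats the allowance: "A 10 % dropout rate of patients has been estimated and considered for the calculation of the number of subjects to be included".

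Section 12.5 also says that the interim analyses are counted on patients who completed the study and that only the final analysis carries the inflation. Section 12.7 repeats this, with interims at 190 and 378 completed patients.

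The protocol treats a patient without a 6-month mRS in more than one way:

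- Section 12.6: patients who leave through loss to follow-up or death are not replaced and "will be considered as non responder patients in the main analysis of primary criterion". Only resignation takes a patient out of the primary analysis. The section then foresees 10% non-evaluable patients.
- Section 12.1 (treatment of missing data): the last recorded mRS, at ICU discharge, is carried forward. The patient is a non-responder only if no mRS exists.
- Sections 12.2.1 and 12.3: loss to follow-up is handled by last observation carried forward, with multiple imputation alongside.

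No section says how much of the 10% is loss and how much is resignation.

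**The concern.** Dividing by one minus the drop-out rate is the right correction when drop-outs disappear from the analysis and those who remain still show the assumed rates. It is not the right correction when drop-outs stay in the denominator as failures. Both response rates then shrink, and so does the difference between them. Carrying an earlier mRS forward also keeps lost patients in the denominator.

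The quoted power of 0.80 therefore belongs to one particular make-up of the 10%, which the protocol does not state. If part of the 10% is loss, or if loss comes on top of it, a true 11-point benefit would be missed more often than the 20% the design accepts.

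**Working it through.** **Inputs.** From 12.5: rates 0.65 and 0.76; one-sided alpha 0.025; looks at 95, 189 and 284 per arm; efficacy limits -3.7103, -2.5111 and -1.9308; futility limits 0.2701 and -1.1224, binding; 315 per arm after inflation. From 4.2.4: 1:1 allocation. Assumptions that the protocol does not state: 65% and 76% are rates among completers, and loss is equal in the two arms.

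**Step 1: reproduce the plan's figure.** Simulating the three looks with a pooled z test for two proportions, 284 per arm, gives power 0.80 against the stated 0.8016. The inflation is 284 / 0.9 = 315.6, stated as 315. Both figures are sound as computed.

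**Step 2: what scoring losses as failures does.** With 10% lost in each arm:

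- control: 0.65 × 0.9 = 0.585
- cilostazol: 0.76 × 0.9 = 0.684
- difference: 0.684 - 0.585 = 0.099, instead of 0.11

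A single-look check without a computer uses power = Φ[(Δ - 1.96·SE0) / SE1], where SE0 is the pooled and SE1 the unpooled standard error.

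- 284 per arm, 0.65 vs 0.76: SE0 = √(2 × 0.705 × 0.295 / 284) = 0.0383; SE1 = √((0.2275 + 0.1824) / 284) = 0.0380. Power = Φ(0.921) = 0.82.
- 315 per arm, 0.585 vs 0.684: SE0 = √(2 × 0.6345 × 0.3655 / 315) = 0.0384; SE1 = √((0.2428 + 0.2161) / 315) = 0.0382. Power = Φ(0.623) = 0.73.

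The 31 extra patients per arm do not make up for the smaller difference.

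**Step 3: the three-look design with interims on completers.** The first two looks use 95 and 189 completers per arm at the undiluted rates. At the final look, lost patients enter as non-responders and resigned patients are absent.

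| Make-up of the drop-out | Final look per arm | Power |
|---|---|---|
| 10% resigned, none lost | 284 completers | 0.80 |
| 5% lost, 5% resigned | about 299, of whom 15–16 are failures by loss | 0.78 |
| 10% lost, none resigned | 315, of whom 31 are failures by loss | 0.75 |
| 10% resigned, then 2% of the rest lost | 284, of whom 6 are failures by loss | 0.79 |
| 10% resigned, then 5% of the rest lost | 284, of whom 14 are failures by loss | 0.76 |

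The 0.75 lies a little above the single-look 0.73. The early looks are undiluted and can still stop for efficacy, and the final limit is 1.9308 rather than 1.96 in absolute value.

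**Step 4: the carry-forward rule.** The protocol gives no response rate at ICU discharge, so this is a range. With 10% lost, interims on completers, and carried values favourable in 20% to 40% of lost patients equally in both arms, power is 0.75 to 0.76. If the carried values already showed the full 65% versus 76%, it would be 0.82.

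**Step 5: if losses also entered the interim looks.** Using 58.5% vs 68.4% at every look, with looks at 95, 189 and 315 per arm, power is 0.69. This is not the interim rule in 12.5 and 12.7.

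**The case against.** The strongest reply is that section 12.6 separates the two groups and then foresees 10% non-evaluable patients. Read in place, the 10% can mean those who exit. Then about 284 per arm remain and power is 0.80. This reading is open, and it rules out a flat statement that the design lacks 80% power. It leaves no allowance for loss, however, although 12.6 itself says that a single assessment at 6 months could lead to loss. It also sits uneasily with the general drop-out wording in 12.5 and 5.8.3.

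Four further points limit the concern:

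- A reader might take non-response as the plan's only rule for lost patients. Sections 12.1 and 12.2.1 carry the ICU-discharge mRS forward, and section 5.2 collects that score for this purpose. Power under that rule depends on what the carried values show.
- A reader might infer a fall to 0.69. That requires losses to be diluting the interim looks, whereas 12.5 and 12.7 count the interims on completed patients.
- The 10% is stated as a ceiling, and 12.6 expects close monitoring to limit loss. With 5% lost and nobody resigning, power is about 0.79.
- If 65% and 76% already count losses as failures, there is no dilution. The protocol does not say so, and on that reading inflating for losses would be unnecessary.

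Deaths add nothing to the problem: they are mRS 6 and belong to the assumed rates already.

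**Conclusion.** The concern holds as a conditional one. The inflation in 12.5 assumes removal, 12.6 assumes retention as failure, and 12.1 and 12.2.1 assume carry-forward. At the planned 10% and under the 12.6 rule, 0.80 is right only if every drop-out is a resignation and nobody else is lost. Otherwise power lies between about 0.75 and 0.79 for the splits examined. At the low end, the chance of missing a true 11-point benefit rises from 20% to about 25%.

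These figures rest on 65% and 76% being completer rates, equal loss in both arms, and interims on completers. The documents do not support a claim that the division is miscalculated, that power is 0.69 under the planned interims, or that 80% power is lost whatever the 10% means. The defect is an undefined drop-out term combined with conflicting rules for a lost patient. It should be fixed, but it does not undermine the design.

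**What to change.** - Reconcile sections 12.1, 12.2.1, 12.3 and 12.6 so that a patient lost to follow-up has one defined primary outcome.
- In 12.5, split the 10% into resignation (leaves the analysis) and loss (stays in under the chosen rule), and use the same terms in 5.8.3 and 12.6.
- State whether 65% and 76% are rates among completers or already count losses as failures.
- Re-run the simulation with 315 per arm, the chosen rule at the final look and interims on completers, and report that power beside the 0.80 for 284 evaluable patients per arm. If the 12.6 rule is kept and the rates are for completers, the statement might read: about 0.78 with 5% loss and 5% resignation, and about 0.75 if all 10% are losses.

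The cost is one simulation run and a text amendment to these sections. Restating the power needs no extra patients.
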